1.4 OBJECTIVES AND ENDPOINTS

OBJECTIVES	ENDPOINTS
Primary:	
To compare change from baseline in mean number of days per month with significant pain or pressure between treatment and placebo groups at 4-6 months.	Change in mean number of days per month with significant midfacial pain or pressure (defined as greater than 4/10) from baseline to 4-6 months
Secondary:	
To compare change from baseline in mean number of days per month with significant pain or pressure between treatment and placebo groups at 1 month and 3 months.	Change in mean number of days per month with significant midfacial pain or pressure (defined as greater than 4/10) from baseline to 1 month and 3 months.
To evaluate the efficacy of erenumab in reducing mean number of days with facial pain (intragroup change)	Change in mean number of days per month with significant pain or pressure comparing baseline to 1, 3, and 4-6 months within each group.
To evaluate the efficacy of erenumab in reducing burden of rhinosinusitis symptoms	Change in 22-Item Sinonasal Outcomes Test (SNOT-22) questionnaire score from baseline to 1, 3, and 6 months
To evaluate the efficacy of erenumab in improving functional impact of migraine-related facial pain	Change in each of the five domains of the Migraine Functional Impact Questionnaire (MFIQ) from baseline to 1, 3, and 6 months
To evaluate the efficacy of erenumab in improving associated symptoms of nasal congestion and rhinorrhea	Change in average number of days per month with significant nasal congestion or rhinorrhea (defined as greater than 4/10) from baseline to 1, 3, and 4-6 months
To evaluate the efficacy of erenumab in reducing pain medication usage	Change in doses of rescue pain medications taken from baseline to 1, 3, and 4-6 months
To evaluate the efficacy of erenumab in reducing daily pain severity	Change from baseline in mean daily pain score from baseline to 1, 3, and 4-6 months

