8.1 STATISTICAL HYPOTHESES

- Primary Efficacy Endpoint(s):
 - ε To compare change from baseline in mean number of days per month with significant pain or pressure between treatment and placebo groups at 4 to 6 months.

Null Hypothesis: In subjects with idiosyncratic facial pain mimicking rhinosinusitis, the erenumab treatment group is the same as placebo, in terms of the reduction from baseline in mean monthly days with significant pain at months 4 to 6.

Alternative Hypothesis: In subjects with idiosyncratic facial pain mimicking rhinosinusitis, the erenumab treatment group is different than placebo, in terms of the reduction from baseline in mean monthly days with significant midfacial pain at months 4 to 6.

- Secondary Efficacy Endpoint(s):

- ⊖ To compare change from baseline in mean number of days per month with significant pain or pressure between treatment and placebo groups at 1 month and 3 months.
- To compare change in mean number of days per month with significant facial pain between baseline and 1, 3, and 4-6 months within each group
- To compare change in 22-Item Sinonasal Outcomes Test (SNOT-22) between treatment and placebo groups at 1, 3, and 6 months
- To compare change in the Migraine Functional Impact Questionnaire (MFIQ) and its five subdomains between treatment and placebo groups at 1, 3, and 6 months
- To compare change in reduction of rescue medication use between treatment and placebo groups at 1, 3, and 4-6 months
- ⊖ To compare change in the mean number of days per month with significant congestion and rhinorrhea between treatment and placebo groups at 1, 3, and 4-6 months.
- To compare reduction in mean pain score between treatment and placebo groups at 1, 3, and 4-6 months

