8.4.2 ANALYSIS OF THE PRIMARY EFFICACY ENDPOINT(S)

The change in the number of days with facial pain or pressure from baseline to completion of the six-month treatment administration period will be analyzed using a linear mixed-effects model including treatment group, baseline value, scheduled visit, and the interaction of treatment with scheduled visit. Imputation is not planned. If applicable, a first-order autoregressive covariance structure is assumed. Least squares means for each treatment group, standard errors, associated 95% confidence intervals as well as the treatment difference, associated 95% confidence intervals and p-values will be reported. A two-sided significance level of 0.05 is assumed.

Additionally, we will compare the change in the mean number of days per month with significant idiosyncratic facial pain between the treatment group versus the placebo-controlled group from baseline to intermediate time points at one and three months.

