8.4.3 ANALYSIS OF THE SECONDARY ENDPOINT(S)

- The mean number of days per month with significant pain or pressure

This will be compared between baseline and 1, 3, and 4-6 months within each group. This represents an intragroup analysis as opposed to comparing treatment and placebo groups.

- 22-Item Sinonasal Outcomes Test (SNOT-22)

The change in mean scores from baseline for the SNOT-22 survey will be compared at 1, 3, and 6 months. The SNOT-22 is the most widely-used validated sinonasal questionnaire in the otolaryngologic literature.[16] Respondents rate the severity of twenty-two symptoms from a scale of 0 (no problem) to 5 (severe as can be) over the previous two weeks, for a score ranging from 0 to 110. It is self-administered and includes symptoms pertaining to multiple domains, including nasal, extranasal, sleep, and psychological. A minimal clinically important difference has been determined to be 9.[17] Analysis of the SNOT-22 will allow the assessment of changes in specific sinonasal symptoms, such as drainage and congestion, which are thought to be associated with idiosyncratic facial pain.

- Migraine Functional Impact Questionnaire (MFIQ)

The change in mean scores from baseline for each of the five subdomains of the MFIQ will be compared at 1, 3, and 6 months. The MFIQ is a self-administered 26-item questionnaire assessing the impact of migraine on five domains over the previous seven days: physical functioning (5 items), usual activities (10 items), social functioning (5 items), emotional functioning (5 items), and overall functioning (1 item).[18,19] Each item is rated on a 5-point scale, with 5 representing the greatest impact. The scores for each domain will be calculated as the sum of the items.

- Change in number of doses of rescue medication use for facial pain

The change in number of doses of rescue medication use from baseline to 1, 3, and 4-6 months will be compared. The daily data log will enable analysis of frequency, type, and numeric dose of the following rescue medications: triptans, opiates, tramadol, acetaminophen-containing medications, butalbital, antihistamines, non-steroidal anti-inflammatory drugs, decongestants, antibiotics, and steroids. The frequency (number of doses) of rescue medication use will be compared between the two groups at baseline and 1, 3, and 4-6 months

- Mean daily pain score

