The change in mean daily pain score (scale of 0 to 10) will be compared between the treatment and control groups from baseline to 1, 3, and 4-6 months.

- Mean number of days per month with significant congestion and rhinorrhea

Significant congestion and rhinorrhea will be defined as symptom score greater than 4 out of 10. The change in mean number of days per month with significant congestion and rhinorrhea from baseline to 1, 3, and 4-6 months will be compared for treatment and control groups.

Analysis of the secondary endpoints will be performed using the same methods as the primary endpoint.

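### About 23 to 29 between-arm secondary tests are each run at two-sided 0.05 with no order, adjustment or nominal label; with no drug effect, at least one favours erenumab by chance about 15-52% of the time

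*Combined protocol and SAP*

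**What the plan says.** The plan has one primary endpoint, the between-arm difference in change in significant pain days at months 4 to 6. Section 8.4.2 analyses it with a linear mixed-effects model and asks for treatment differences, 95% confidence intervals and p-values. On the level it says: "A two-sided significance level of 0.05 is assumed".

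The secondary comparisons are spread over two sections:

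- Section 8.4.2 adds pain days at earlier times: "Additionally, we will compare the change in the mean number of days per month with significant idiosyncratic facial pain", with the contrast running "from baseline to intermediate time points at one and three months".
- Section 8.4.3 covers the rest. For the sinonasal questionnaire: "The change in mean scores from baseline for the SNOT-22 survey will be compared at 1, 3, and 6 months". For the migraine questionnaire, "each of the five subdomains of the MFIQ will be compared at 1, 3, and 6 months". Rescue doses, mean daily pain score and days with congestion and rhinorrhea are each compared at 1, 3 and 4-6 months.
- Section 8.4.3 closes with: "Analysis of the secondary endpoints will be performed using the same methods as the primary endpoint".

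Section 8.1 lists these under a secondary efficacy heading, and its MFIQ item covers the questionnaire "and its five subdomains between treatment and placebo groups at 1, 3, and 6 months". In section 1.4, six of the seven secondary objectives are worded as evaluating efficacy, for instance "To evaluate the efficacy of erenumab in reducing burden of rhinosinusitis symptoms".

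Nowhere in sections 8.1 to 8.4.4 is there a testing order, an alpha allocation, a multiplicity adjustment, a condition that the primary must succeed first, or a statement that secondary results are exploratory or nominal.

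**The concern.** The secondary endpoints are presented as evidence of efficacy, and each takes over the primary method with its 0.05 level. With more than twenty such tests, one or more small p-values are likely even if the drug does nothing. The plan does not say what may be concluded from them.

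Two situations are at stake. If the primary endpoint fails, nothing written bars a report from presenting one MFIQ domain at one visit as a finding of efficacy. If the primary succeeds, the plan gives no prespecified way to tell which secondary results may be claimed and which are only descriptive.

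**Working it through.** **The plan's own figure.** The documents state no familywise error rate for the secondary endpoints. The only related figure is the sample size in section 8.2, which confirms that 0.05 is spent on a single primary test. With difference 3.0, SD 3.5, two-sided 0.05 and 90% power, the normal approximation gives n per arm = 2 × (1.960 + 1.282)² × 3.5² / 3.0² = 28.6, so 29. Dividing by 1 − 0.10 for dropout gives 32.2, so 33, as stated.

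**Step 1: count the between-arm secondary tests.** The scheduled count uses section 1.3, where SNOT-22 and MFIQ are collected only at screening, Day 90 and Day 180, so their month-1 comparisons cannot be made.

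| Endpoint | As written | As scheduled |
|---|---|---|
| Pain days, months 1 and 3 | 2 | 2 |
| SNOT-22 | 3 | 2 |
| MFIQ, five domains | 5 × 3 = 15 | 5 × 2 = 10 |
| Rescue doses | 3 | 3 |
| Mean daily pain score | 3 | 3 |
| Congestion and rhinorrhea days | 3 | 3 |
| Total | 29 | 23 |

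The as-written total rises to 32 if an overall MFIQ score is also tested, as section 8.1 may imply, and to 35 if congestion and rhinorrhea are also tested separately. The within-group comparisons (3 time points × 2 arms = 6) and the subgroup repeats in section 8.4.4 are not in any of these counts.

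**Step 2: independent tests (upper bound).**
- Either direction, 1 − 0.95^k: 1 − 0.95^23 = 69.3%; 1 − 0.95^29 = 77.4%.
- Favouring erenumab, 1 − 0.975^k: 1 − 0.975^23 = 44.1%; 1 − 0.975^29 = 52.0%.

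**Step 3: correlated tests.** The tests come from the same patients, so correlation is expected. The documents give no value, so it is an assumption. For k test statistics with common correlation ρ, z = 1.96, and g standard normal:
- Either direction: 1 − E{[Φ((z − √ρ·g)/√(1−ρ)) − Φ((−z − √ρ·g)/√(1−ρ))]^k}
- Favouring erenumab: 1 − E{[Φ((z − √ρ·g)/√(1−ρ))]^k}

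| ρ | Either direction, k = 23 / 29 | Favouring erenumab, k = 23 / 29 |
|---|---|---|
| 0 | 69.3% / 77.4% | 44.1% / 52.0% |
| 0.3 | 58.2% / 65.1% | 30.3% / 34.4% |
| 0.5 | 44.9% / 49.9% | 22.5% / 25.1% |
| 0.7 | 30.6% / 33.4% | 15.3% / 16.7% |
| 0.8 | 23.5% / 25.3% | 11.7% / 12.7% |

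**Step 4: a more structured correlation.** A simulation of 200,000 draws used separate assumed correlations: 0.5-0.8 across visits, 0.3-0.7 between endpoints and 0.6-0.9 between MFIQ domains. It gave 31-63% in either direction and 15-34% favouring erenumab.

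**Step 5: expected number.** With no effect, the expected count of significant results is 23 × 0.05 = 1.15 to 29 × 0.05 = 1.45. Half of these, about 0.6 to 0.7, would favour erenumab.

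**The case against.** The best defence is that a 66-patient, single-site trial with one clearly named primary endpoint need not adjust its secondary tests. Section 8.1 states null and alternative hypotheses only for the primary and lists the secondary items as comparisons. No section gives a rule by which a secondary result establishes efficacy. Section 8.4.2 already requires differences with 95% confidence intervals, section 8.4.3 extends this to the secondary endpoints, and it cites a minimal important difference of 9 for SNOT-22. A reader therefore has more than p-values to go on.

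Much of this stands. Leaving secondary tests unadjusted is acceptable when the plan says that they support no efficacy claim. This plan does not say so, and its objectives point the other way.

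Three stronger readings are tempting and are not supported:

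- **That 31-77% is the chance of a false efficacy result.** The tests are two-sided, so this figure also counts differences favouring placebo. The chance of one favouring erenumab is 15-52%.
- **That the trial's main conclusion is compromised.** The primary is a single test at 0.05, and the secondary tests do not alter its error rate.
- **That the 1- and 3-month pain-day comparisons are extra primary tests because they sit in section 8.4.2.** Sections 1.1, 1.4 and 8.1 all label them secondary. Their position is an editorial matter.

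**Conclusion.** The concern holds for the secondary family only. Taking the shared methods to include the 0.05 level, 23 feasible to 29 written between-arm tests run with no rule on what may be claimed from them.

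Both ends of the error ranges rest on assumption. The top needs 29 independent tests, which is implausible for repeated visits and related domains in the same patients, and six of the 29 cannot be run as scheduled. The bottom rests on a correlation of 0.7; at 0.8 both ranges would start lower. Even at 0.7, a chance result favouring erenumab has a probability of 15-17%, about six times the 2.5% for a single test. That is enough to need a stated rule.

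**What to change.** Add one paragraph to section 8.4.3 stating that:

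1. Secondary endpoints are tested for efficacy claims only if the primary endpoint is significant at two-sided 0.05.
2. They are then tested in one short fixed sequence, each step at 0.05, stopping at the first failure. The sponsor chooses the order and records it before unblinding. An example is pain days at month 3, mean daily pain score at months 4-6, rescue use at months 4-6, then SNOT-22 at 6 months. All of these are collected under the current schedule.
3. All other secondary, MFIQ-domain, within-group and subgroup results are reported as estimates with 95% confidence intervals, with any p-values labelled nominal and no efficacy claim.

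The primary must be named as the first gate. If the sequence began at a secondary endpoint without it, the chance of an error across the primary and the first step could reach 1 − 0.95² = 9.75% if the two were independent. With the gate, the chance of any false claim in the primary and the sequence together is at most 5%.

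The cost is one paragraph, with no added patients and no change in primary power. The downside is that some nominally significant secondary results can no longer be claimed, and an early failure in the sequence blocks the later steps. Moving the 1- and 3-month text from 8.4.2 to 8.4.3 would be tidier but is optional.

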8.4.4 SUB-GROUP ANALYSES

The primary and secondary endpoints will be assessed in subgroups based on facial pain/pressure severity, as measured by frequency of facial pain/pressure days. We hypothesize that subjects with greater severity (definition to be determined) will show greater benefit with the study medication.

9 SUPPORTING DOCUMENTATION AND OPERATIONAL CONSIDERATIONS

9.1 REGULATORY, ETHICAL, AND STUDY OVERSIGHT CONSIDERATIONS

9.1.1 INFORMED CONSENT PROCESS

All potential study participants will be given a copy of the IRB-approved informed consent to review. The principal investigator, study coordinator, or authorized key personnel will explain all aspects of the study in lay language and answer all questions regarding the study. If the participant decides to participate in the study, he/she will be asked to sign and date the Informed Consent document. No study procedures will be conducted without prior written informed consent. Subjects who refuse to participate or who withdraw from the study will be treated without prejudice.

9.1.1.1 CONSENT/ASSENT AND OTHER INFORMATIONAL DOCUMENTS PROVIDED TO PARTICIPANTS

Study participants will be given a copy of the written informed consent, along with instructions for who to call with questions or potential adverse reactions. Instructions will also be given for completing questionnaires and the daily pain and medication log.

9.1.1.2 CONSENT PROCEDURES AND DOCUMENTATION

Documentation of the consent process will be entered in the study participant's electronic health record.

9.1.2 DISCONTINUATION AND STUDY STOPPING RULES

Subjects will be given the opportunity to withdraw from the study at any time. Every effort will be made to obtain follow-up information. Subjects who discontinue prematurely will be asked to return for a final follow-up visit either in person or by phone.

In the event of serious adverse events felt to be possibly related to erenumab and occurring in more than 3 study patients, the study will stop enrollment and the FDA will be notified for review and feedback. A single patient death possibly related to erenumab will also stop the study.

9.1.3 CONFIDENTIALITY AND PRIVACY

Study records that identify subjects will be kept confidential as required by law. Federal Privacy Regulations provide safeguards for privacy, security, and authorized access. Except when required by law, subjects will not be identified by name, social security number, address, telephone number, or any other direct personal identifier in study records disclosed outside of Duke University Health System (DUHS). Anonymized data may be shared with the maker of erenumab in accordance with the executed agreement.

Participant confidentiality is strictly held in trust by the sponsor-investigator, sub-investigators, study staff, and their agents. This confidentiality is extended to cover use of medical records related to medical history images in addition to any study information relating to participants.

The study monitor or other authorized representatives of the sponsor-investigator may inspect all study documents and records required to be maintained by the sponsor-investigator (Principal Investigator), including but not limited to, medical records (office, clinic, or hospital) for the study participants. The clinical study site will permit access to such records.

Electronic data will be stored in a private folder housed in a secure server behind the Duke University Medical Center firewall. Paper documents including but not limited to CRFs, questionnaires and original signed ICFs will be kept in a locked file in the HNSCS Research Office, which is locked when not in use. Research data such as the data dictionary and de-identified 3D imaging data and analysis will be stored on a secure, password-protected desktop computer at Duke University. Only study staff listed as key personnel will have access to study data.

This project uses the REDCap Twilio integrated functionality. This module enables a research study to make and receive voice calls and SMS text messages, both to and from survey respondents. A REDCap and Twilio account are linked together. When a user indicates that an SMS (text) or a call should be sent to a cell phone, REDCap requests that action through Twilio. When a user responds, Twilio relays that information back to REDCap. The data is stored in the REDCap database. Twilio does not store any data nor does it keep a log of its actions.

It is important to understand that this feature utilizes the third-party service [Twilio.com](https://www.twilio.com), which means that all voice calls and SMS messages will be routed through Twilio's servers. However, REDCap goes to great length to ensure that voice call records and SMS transcriptions do not stay in Twilio's logs but are removed shortly after being completed. This is done for security and privacy concerns (e.g., HIPAA), in which your survey participants' phone numbers and their survey responses do not get permanently logged on Twilio's servers but instead remain securely in REDCap.

The REDCap Twilio module is managed by the Biomedical Informatics group in the Institute for Clinical and Translational Science at the University of Iowa. Twilio uses two-factor authentication to access the application administratively. The integrated module can only be turned on by a REDCap Administrator. Twilio configuration is managed by a REDCap administrator. The integration requires 'inspectors' be turned off at the Twilio level to ensure no logging data is retained.

This study uses the **Survey as SMS conversation** functionality. When participants take an SMS survey, questions are asked one at a time as an SMS text message conversation/thread. Participants may respond with any kind of alpha-numeric text for SMS survey. Survey as a SMS text conversation is not encrypted communication. HIPAA information will not be collected via this method, unless a special exception is granted. The data being collected using this method reflects what is included in the protocol submission and approved. Appropriate language will be included in the subject consent to

inform subjects of the potential risk of unencrypted communication. Only REDCap administrators are allowed to enable the Twilio option to initiate a survey as an SMS conversation.

This study will also use the **Survey invitation link via SMS** which allows for encrypted communication. Once the participant clicks on a link to the survey, they fill out that survey in a secure environment (<https://>) on the mobile device, just as they would on a desktop or laptop browser. HIPAA information may be collected using this method. The data being collected using this method reflects what is included in the protocol submission and approved by the IRB.

During data collection, subject identifiers and relevant data elements will be recorded. Then, study-specific identification numbers will be assigned to each subject. Prior to dissemination of any data beyond the Duke secure servers or firewall, all identifiers will be stripped from the database and data will only be referenced by the study-specific identification numbers. A master log, which links the study-specific identification number to the study subject, will be generated. The master log will be stored in the study-specific, private electronic folder and will be accessible only to key personnel.

9.1.4 FUTURE USE OF STORED DATA

Data may be available for future research provided the data is de-identified and has obtained sufficient IRB approval for use. The IRB approved ICF will include language alerting subjects that de-identified data collected as part of this study may be used for future research.

